4.2 Exclusion Criteria

- Have diabetes measured or by self report
- Have CKD measured or by self report
- Pregnancy at time of enrollment by self report

- Too cognitively impaired to provide informed consent and/or complete the study protocol measured by mini mental status exam
- Institutionalized or too ill to participate (i.e. terminally ill, incarcerated, in psychiatric or nursing home facility) by self report
- Plan to move out of the area within 12 months of enrollment by self report
- Not a patient under the care of a provider for their hypertension at a participating site by self report
- Previously participated in the *APOL1* qualitative pilot study or have previously undergone *APOL1* testing

5. RECRUITMENT AND ENROLLMENT PROCEDURES

5.1 Participating Sites

Recruitment will be from primary care clinics within Mount and Institute for Family Health.

5.2 Provider Recruitment, Consent and Survey

We will present the study to providers at participating clinics and ask them to complete a short form consent explaining the purpose and the voluntary nature of their participation in the study. They will also receive the GUARDD APOL1 Provider Baseline Survey to be completed upon enrollment where we will ask questions about their current knowledge of genomics and personalized medicine and clinical decision support. At this time, we will also ask providers to give us permission to contact their patients who may be eligible to participate in the randomized trial and to have a recruitment letter sent to their patients signed by them or their practice. Providers who prefer to have a recruitment letter sent from them will provide a signature on a copy of the letter. As new providers join practices, we will also obtain their permission to contact their patients and ask them to complete the survey.

We will ask providers at participating sites to complete the GUARDD APOL1 12 Month Follow-Up Survey approximately 12 months after study enrollment. This questionnaire will contain similar questions asked at baseline, in addition to reactions to any clinical decision aids or exposure to APOL1 genetic testing over the course of the study. A list of participating providers will be kept by the study team to track completion of questionnaires and training attendance at the different study sites.

5.3 Participant Identification and Recruitment Strategies

Participant Identification

Electronic Health Record (EHR) Data Runs for Eligible Participants

Potential participants will be primarily identified through data runs using the inclusion criteria mentioned above. Lists with PHI identifying potential participants are emailed to the Program Manager via a secure, password protected Excel file. Participant's, date of birth, address and phone numbers, primary care provider name and clinic site extracted from the EHR are imported into the Redcap study database.

Referral

Participants may self-refer from any advertisement materials (posters, flyers). They may also be referred by a family member or friend, or by a provider who has agreed to allow their participants to participate in the study.

If a participant is referred, the Study Coordinator should check the REDcap database to ensure the participant is not already in the database and proceed accordingly.

Participant Recruitment

There are three main scenarios for recruitment:

- **Via recruitment letter:** Study Coordinators will be assigned participants (from the list of potentially eligible participants obtained through an Epic data run) and mail study recruitment letters to them. Letters are mailed in a bright blue envelope and postmarked with the GUARDD and clinic site logo to assist participants with recall and recognition. Participants can call us upon receiving the letter and they will then be screened for study eligibility. Study Coordinators will wait approximately 2 weeks after this mailing for a participant to return the letter refusing to participate, to call them, or to meet them at an upcoming clinic visit.
- **During a phone call:** If a participant does not return the refusal letter or contact us within 2 weeks of mailing, the Study Coordinator assigned to him/her will contact the participant by telephone. Using the recruitment phone script they will remind them about the letter that was mailed to them, introduce or reintroduce the study, screen them for eligibility, and answer any questions about the study.
- **During a clinic visit:** The Program Manager will receive a weekly list of which participants/potentially eligible participants have a scheduled clinic appointment and will notify the Study Coordinator assigned to that clinic site so s/he will plan to meet the participant at that time. The clinical Study Coordinator will discuss the study with the participant, screen them for eligibility, and answer any questions about the study.

Study Coordinators will then schedule all eligible and interested participants for a baseline visit. A baseline visit may occur at the time of recruitment (if approached at a clinic visit) or at a later date.

5.4 Screening Procedures

Study Coordinators will use a recruitment script during recruitment phone calls or clinic intercepts to inform the potential participant about the study and screen participants for eligibility using the study inclusion/exclusion criteria. If the participant is eligible and interested, a baseline visit will be scheduled that same day or for a future date.

5.5 Participant Consent Process

If a participant is interested and eligible, Study Coordinators will review the consent document at the start of the baseline study visit. Prospective research participants will have the opportunity to ask questions before providing written consent. Study Coordinators will provide the participant with a copy of the consent document. If the individual chooses not to sign the consent form, the Study Coordinator will inform him/her they are unable to participate in the study. The participant will also be provided the option to be contacted for future research.

5.6 Participant Discontinuation/Withdrawal from the Study

Participants may stop participating or withdraw from the study at any point in time. All information and data collected from the participant up to that point can be used in the study. Withdrawal of consent to participate in

the research study can be verbal or in writing. Study Coordinators should attempt to obtain a reason for withdrawal from the participant and record it in the study database.

Participants may withdraw from the study at any time by writing to the PI or by verbally informing the study coordinator or Program Manager. Any data collected up until withdrawal may be analyzed for study purposes but no new information will be collected.

5.7 Lost to Follow-Up

Losses to follow-up may be minimized and retention maximized through various mechanisms, including offering study visits during evening and weekend hours, collecting information for and contacting family members when participants cannot be reached, approaching research participants at clinic appointments, and completing surveys over-the-phone (although research participant should still attend study visits for blood pressure measurement). Certified letters may also be sent to those not reached by phone. Study Coordinators can confirm the best contact information for the participant at each study visit. Study Coordinators may also obtain permission to contact participants via text message or email and may send additional correspondence during the study. Participants may be assigned to a specific Study Coordinator at the site in order to maintain continuity and build rapport.

5.8 Risks

This research presents minimal risks to participants. Possible risks are described below.

Blood Pressure

Participants may feel some arm pressure when the blood pressure cuff is briefly inflated.

Blood Draw

The risks of a blood draw include pain, bruising, and the slight possibility of infection at the location of needle insertion. Some participants may feel dizzy or may faint during or after a blood draw.

Saliva Collection

Some people may feel discomfort because they cannot eat, drink, smoke or chew gum for 30 minutes before giving a saliva sample.

Psychological Distress Learning of Test Results

Results of the genetic test may show that a participant is at an increased risk of kidney disease. This knowledge may cause anxiety or psychological distress. Study staff will be trained to recognize anxiety and psychological stress and talk through this discomfort with the participant. All participants will have the option to speak with a genetic counselor if they choose.

5.9 Benefits

Participants may not receive any benefit from taking part in this research. Others may not benefit either. However, participants and their providers will obtain clinically-relevant genomic risk information to guide evaluation and treatment of hypertension and renal functioning, thus providing some indirect benefit to participant health.

5.10 Costs to the Participants

The costs of study-related genomic testing are covered by the study and will not be billed to participants. Taking part in this research study may lead to minor added costs including, for example, transportation to attend study visits. Participants (and/or their health care payer) will still be billed for the costs of their regular medical care that are not part of this study.

5.11 Compensation to Participants

Study participants will receive \$40 in gift cards (to a variety of local retailers) at each of the Baseline, 3 Month and 12 Month follow-up visits. If a participant withdraws from the study before all visits are completed, they will be paid for any completed visits. If a participant is able to complete a survey over the phone for a follow up visit, but is unable to come in-person for a blood pressure measurement within the visit window, they will only receive a \$20 gift card, which may be mailed to them at the address they provide.

6. STUDY PROCEDURES

6.1 Provider Surveys

Prior to first enrollment at a site, at one of their existing meetings, providers will be asked to complete a consent form to contact their potentially eligible participants and to complete the Baseline Provider Survey to assess demographics, knowledge, beliefs and practices around *APOL1* testing specifically and genetic testing more generally. This survey is anonymous. A GUARDD clinical champion will present the study to the providers of each site

6.2 Baseline Study Visit

Consent

The Study Coordinator will follow appropriate consenting protocol to consent interested and eligible participants.

Survey

After participants sign the informed consent, the Study Coordinators will confirm participant contact information and administer the GUARDD Baseline Survey using the REDCap database. Study Coordinators also have the option of administering surveys on paper and entering the responses in the RedCap database at a later date.

Biological Measures

Study Coordinators will obtain blood pressure using study specific protocols (outlined in the MOP) for blood pressure measurement using the BPTru portable blood pressure machine (29). If after several attempts, the study coordinator is unable to obtain an arm blood pressure measurement because the participant's arm is too large for the arm cuff or another reason, blood pressure will be measured using the Omron HEM 670IT wrist monitor and make a note in the participant's Redcap record. Study Coordinators will record the second and third blood pressure measurement in which will calculate the average blood pressure reading.

Study Coordinators will also measure participant height using the Charder HM200P portable stadiometer (at Baseline Visit only) and weight using the Detecto DR550C portable high capacity platform scale and input this information into the RedCap database which will calculate BMI.

Study Coordinators will record the average blood pressure and participant height and weight on the Personal Health Screening Form along with estimated dates for study follow up for the participant's personal records.

If the participant has a blood pressure reading greater than 190/110 during the study visit, study staff must complete an Elevated Blood Pressure Note for the participant, record the reading on REDCap, inform participant that they have very high blood pressure and strongly advise that they get urgent and appropriate evaluation and care from a healthcare provider. Study staff must also inform study PIs.

Specimen Collection

Participants will be randomized via the REDCap randomization tool using a stratified randomization scheme by clinical site in a 7:1 ratio of immediate or delayed *APOL1* genetic testing. The Study Coordinator informs the participant of their randomization outcome. A blood (preferred) or saliva sample is collected from participants randomized to immediate testing by the Study Coordinator. Study Coordinators will obtain a genetic sample for control participants at their 12 month visit. Participants are informed that their result will be ready in 2-4 weeks.

The baseline visit will take approximately 1.5 hours to complete. Participants will receive \$40 in gift cards when they have completed their baseline visit.

6.3 Follow-Up Assessments

All participants will be advised that they will be contacted to complete a follow-up study visit at 3 months and 12 months after enrollment (duration of the observation period). During follow-up visits, Study Coordinators will follow study protocol (outlined in the MOP) to conduct surveys, measure blood pressure, and obtain participant weight in order to calculate body mass index. They will enter this data directly into REDCap using tablets/laptops. The follow-up visits will take approximately 45 minutes to complete. Participants will receive a \$40 gift card for each follow-up visit completed.

Follow-up visits will be completed between 14 days prior and one month after the projected follow-up date (projected 3 month study visit due date = 3 months from date of baseline visit completion; projected 12 month study visit due date = 12 months from date of baseline visit completion). Whenever possible, participants will meet with the same Study Coordinator for follow-up visits to maintain continuity.

If the participant has a blood pressure reading greater than 190/110 during any follow up visit, study staff must complete an Elevated Blood Pressure Note, inform the participant that they have very high blood pressure and strongly advise that they get urgent and appropriate evaluation and care from a healthcare provider. Study staff must also inform study PIs.

6.4 Specimen Collection

Blood Specimen: At the baseline visit, Study Coordinators will consent participants if not previously consented, administer the baseline survey, take 3 blood pressure readings, measure participant height and weight and, if

trained in phlebotomy, collect 1 purple tops EDTA tube (approximately 3-5 mL) of venous blood from participants willing to provide a blood sample. If the Study Coordinator is not trained in phlebotomy, the participant will have their blood drawn by a trained phlebotomist. Participants will then be randomized to the Control or Intervention arm. Study Coordinators will label the tube with the participant ID, date of birth, sex and the date sample was collected, and follow the MOP for the collection, storage, and delivery of the sample to the laboratory.

Saliva Specimen: In the event that it is not possible to obtain a blood sample or participants prefer saliva collection, Study Coordinators will use an Oragene OG-500 kit to collect a saliva sample. They will label the sample and follow the saliva collection protocol for the collection, storage, and delivery of the sample to the laboratory as outlined in the MOP.

6.5 Specimen Transfer and Genetic Testing Procedures

Study Coordinators should store and directly transport specimens to the Mount Sinai Genetics Testing Laboratory, a Clinical Laboratory Improvement Amendments (CLIA)-certified laboratory, according to procedures outlined in the MOP. Specimens will be accepted by the lab twice a week and processed on a weekly basis.

The *APOL1* G1/G2 genotype testing incorporates Polymerase Chain Reaction (PCR) and multiplex Allele Specific Primer Extension (ASPE) with Tm Bioscience's proprietary Universal Tag sorting system on the Luminex® 100 xMAP™ platform. Three SNP genotype in exon 6 are tested (RS73885319, RS60910145, RS71785313) to determine G1 and G1 allele status. To validate this genotyping method, at least three intra-assay and inter-assay runs involving 50 positive controls and 8 negative controls were performed. The positive control DNAs include samples which are heterozygous or homozygous for G1 and G2 genotypes. Negative controls are WT DNA for G1 and G2 alleles. Assays were 100% concordant reproducibly between the Luminex genotyping method and Sanger sequencing for each of the control samples.

6.6 Return of Genetic Results

Result reporting will occur approximately 1-4 weeks after the samples are obtained (see Fig. 1 Study flow chart). The laboratory will notify the study Program Manager of when results are ready to be returned. The Program Manager will in turn alert Study Coordinators. Return of results will be done by their assigned Study Coordinators. Study Coordinators will be trained by [name], Director of Mount Sinai Genetic Counseling Program, to return risk assessment results and recommendations. They will use a Return of Results Script for this visit. *APOL1* negative participants will have their tests results returned by phone (participants in the formative study said they did not want to come back in person for a negative results) and those that are *APOL1* positive will be scheduled for an in person return of results visit. If an in person return of results visit is not able to be scheduled for an *APOL1* positive participant, we will offer the participant the opportunity to receive their results over the phone. During return of results, the Study Coordinator will disclose the genetic test result, provide simple, clear information and use "speak back" or "teach back" technique to maximize participants' comprehension of their result. In addition to verbal ROR, participants will also receive lay explanations of their test results in writing and the educational booklet about *APOL1*, blood pressure and kidney

disease. *APOL1* positive participants will review the informational booklet at the time of their return of results, *APOL1* negative participants will receive their written test results and informational booklet in the mail.

If we are unable to return an *APOL1* positive test result to the participant for at least 3 months we will notify their primary care provider so that the result can be noted in their electronic health record and the participant can be notified of their results when they get in contact with their provider, even if that is after the study has ended.

All participants will be given the option to speak to a genetic counselor after their return of results in person or by telephone, at no charge. If a participant chooses to speak with a genetic counselor, the Study Coordinator will contact the genetic counselor on behalf of the participant, and the genetic counselor will then follow-up directly with the participants.

Once a result is returned to the participant, the Study Coordinator completes the corresponding fields in Redcap that prompts CLIPMERGE to fire a Best Practice Alert (BPA) in the participant's electronic health record the next time a primary care provider opens it. The BPA will pop up once per unique provider. A provider can choose to open the BPA and has the option of clicking on and viewing and printing information for the participant and information for him/herself. In addition to the BPA, the lab will also place a copy of the *APOL1* genetic test results in the participant's electronic medical record. Electronic Health Record Data Extraction

6.7 Electronic Health Record Data Extraction

Electronic health data relevant to the study endpoints will be pulled for the period of 12 months prior to randomization and 12 months after randomization for all enrolled participants.

Figure 2. *APOL1* positive BPA Alert

Genomic Medicine – GUARDD Study

POSITIVE RESULT:
This patient has INCREASED RISK for End Stage Kidney Failure according to *APOL1* genetic testing (result: G1/G1)

Evidence suggests that good blood pressure control and renal function testing may forestall kidney failure.

Recent blood pressure readings were:
12/15/2011 3/23/2012 6/1/2013
140/90 130/85 120/80

[Click here for provider information](#)

[Click here for patient materials](#)

Note: These results will be filed under Labs / Genetics.

6.8 Study Retention

Carefully trained, dedicated Study Coordinators that are from the same demographic groups and neighborhoods as participants will recruit participants, and will facilitate retention using relationship building, continuity with their assigned participants, sending personalized birthday and holiday cards, sending a 6 month check in postcard, placing a 9 month check in phone call, and collecting multiple contacts and modes of contact (e.g., phone, mail, text, email, intercepting at upcoming clinical appointments) from study participants. They will also “intercept” participants at clinical visits should they have clinical visits during the follow-up windows. If participants are unable to come to the practice for the entire visit, they can be surveyed by phone and come for blood pressure check, and if they cannot come at all, they can be surveyed by phone.

7. SAFETY ASSESSMENT AND MONITORING

The GUARDD Study is an observational-type study that does not include a drug or device intervention. For this reason, no adverse events will be collected or recorded in the study database. Adverse events suspected to be related to study interventions should be reported to the Mount Sinai and Institute for Family Health IRBs according to their local policies.

7.1 Distress from Return of Results

Distress from return of results will be monitored at participant visits. If the participant seems overly distressed by the outcomes of the genetic test results, the Research Coordinator will offer the participant the opportunity to speak to the genetic counselor. If the genetic counselor is not immediately available, the Research Coordinator will help coordinate a phone call or meeting with the genetic counselor based on participant’s preference. The study coordinator will also inform the Project Manager and PI, document the event in the notes field of the participant’s study database record, and follow-up with participant.

7.2 Elevated Blood Pressure Readings

If systolic blood pressure exceeds 190 mm Hg or diastolic exceeds 110 mm Hg during any study visit, the participant will be strongly advised to seek urgent and appropriate evaluation and care from a healthcare provider. The Research Coordinator may facilitate this by assisting the participant in contacting their primary care provider, urgent care, or clinic staff on site including the Principal Investigator (if study visit is taking place in a clinical setting) and by completing the Elevated Blood Pressure Note that participants may share with their provider.

8. STATISTICAL ANALYSIS PLAN AND SAMPLE SIZE

8.1 Sample Size Determination

The study will randomize 2050 patients to either immediate or delayed genetic testing in a ratio of 7:1 respectively. We anticipate that of the 1800 patients who will be tested immediately approximately 250 will test positive. For this aim, we hypothesize that APOL1 positive patients will achieve 40% correct utilization of serum creatinine and/or urine albumin tests for “standard renal care” in patients with hypertension, compared to

30% for APOL1 negative patients. With an estimated 250 APOL1 positive and 1550 APOL1 negative we will have 87% power to detect the difference of interest using a two sided chi-square test.

Power calculations for this sub-aim are based on reduction of systolic blood pressure at three months after enrollment. For patients who test APOL1 positive we anticipate a 5 mmHg reduction in systolic blood pressure, compared to no change in patients who test APOL1 negative. Assuming that the standard deviation for differences in blood pressure between baseline and 3 month in both arms is 20 mmHg, a total of 250 patients testing positive and 1550 testing negative provides approximately 95% power to detect a difference of 5 mmHg in SBP between these two groups. If the standard deviation is larger than assumed, say 25 mmHg, power will still exceed 80%. Power is based on a 0.05 level two-tailed t-test of the difference in SBP at 3 months.

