Several reports demonstrate that *APOL1* risk alleles are highly significantly associated with CKD attributed to essential hypertension in non-diabetic AASK participants, and the genetic association was most robust in individuals with progressive renal functional decline [\(22\)](#) (see our AASK Cohort data in Table 1). Because of the overwhelming strengths of the evidence, we propose to establish *APOL1* genomic risk status in non-diabetic AA participants and to incorporate the *APOL1* G1/G2 risk allele status in a recessive model together with conventional risk factors in CKD and CKD progression advice messages.

Aim III. Conduct a randomized trial assigning eligible participants to immediate genetic testing or delayed genetic testing arms in a seven (immediate testing) -to- one (delayed testing) ratio.

Sub-Aim 3.1: To examine whether increase in practice guideline-appropriate renal laboratory test ordering (renal care endpoint) will be achieved in *APOL1*-positive group vs *APOL1*-negative group.

Sub-Aim 3.2. To examine whether systolic blood pressure will decline more in the *APOL1*-positive group compared with *APOL1*-negative group.

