3.4 Sample Size

The total number of people expected to participate is 2,050. Of the 1800 intervention participants, approximately 250 will test positive. We will thus have approximately 250 high risk, 250 control, and 1550 normal risk participants. The sample size for the study was calculated assuming a 10% improvement in practice guideline-appropriate renal function test ordering in the *APOL1*-positive group (40% estimated) vs. *APOL1*-negative group (30% estimated) to yield 87% power to detect the difference of interest using a two-sided chi-square test. Specifically, this includes measurement of serum creatinine and urine microalbumin. The blood pressure sub-aim, 5mmHg improvement in systolic blood pressure at 3-month follow up in *APOL1*-positive compared with *APOL1*-negative group, can be detected with 95% power.

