8.2 General Statistical Methods

We will use mean and standard deviation to describe continuous variables, proportions for categorical variables; t-tests or analysis of variance (ANOVA) to compare continuous variables, and chi-square or Fisher's exact test to compare categorical variables by groups. To test significance of changes within groups over time, we will use paired t-tests for continuous and McNemar's tests for categorical variables. We will use linear mixed models to test the difference in SBP change over time between *APOL1* positives and negatives by entering the interaction term of time and *APOL1* status and adjusting for confounders, and generalized estimating equation methodology to test the change in controlled SBP status and renal function testing overtime between *APOL1* positives and negatives, and similarly between *APOL1* positives and controls.

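### The 87% power for the renal endpoint is right for a one-time chi-square, but it does not carry over to the GEE test of change, the only method Section 8.2 names for renal testing

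*Combined protocol and SAP*

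**What the plan says.** Section 8.1 sets the renal hypothesis as a difference in proportions: "we hypothesize that APOL1 positive patients will achieve 40% correct utilization of serum creatinine and/or urine albumin tests", against "30% for APOL1 negative patients". The group sizes follow ("With an estimated 250 APOL1 positive and 1550 APOL1 negative"), and then the conclusion that "we will have 87% power to detect the difference of interest using a two sided chi-square test". Section 3.4 repeats the calculation, "assuming a 10% improvement in practice guideline-appropriate renal function test ordering", with the same 40% and 30%. Section 2.1 places both primary comparisons, positive against negative, at three months.

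Two other places point towards change. Sub-Aim 3.1 in Section 1.2 reads "To examine whether increase in practice guideline-appropriate renal laboratory test ordering (renal care endpoint) will be achieved in" positives compared with negatives. Section 8.2 assigns renal testing to "generalized estimating equation methodology to test the change in controlled SBP status and renal function testing overtime between" positives and negatives. Section 8.2 also lists chi-square or Fisher's exact test for categorical variables by group, without naming an endpoint. No renal analysis is designated primary.

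For systolic blood pressure, Section 8.1 takes its standard deviation from the baseline-to-3-month difference. It has no corresponding step for renal testing: no baseline rate, no within-patient correlation and no link function.

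**The concern.** A one-time comparison of 40% with 30% carries the sampling error of one proportion per group. A between-group comparison of change in a yes/no measure carries the error of two proportions per group, reduced only by the correlation between a patient's two measurements. Unless that correlation is high enough, the second test has less power for the same 10-point effect.

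Anyone running the model that Section 8.2 names for renal testing would find one power figure in the plan, 87%, and it was calculated for another test. If the GEE contrast were reported as the main renal result and came out null, the 87% could lend it more weight than it deserves as evidence that disclosure does not alter test ordering.

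**Working it through.** **Inputs from the documents.** 40% and 30%; 250 and 1550 (Section 8.1). Two-sided 0.05 is printed only for the blood pressure t-test ("Power is based on a 0.05 level two-tailed t-test of the difference in SBP at 3 months") and is assumed for the chi-square.

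**Inputs not in the documents, so assumed.** A common baseline testing rate b in both groups; within-patient correlation ρ; two measurements per patient over comparable windows; no dropout. The central case takes b = 30%, the plan's own rate for negatives.

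**Step 1: the plan's figure.**
- Pooled proportion = (250 × 0.40 + 1550 × 0.30)/1800 = 565/1800 = 0.3139.
- Null SE = √[0.3139 × 0.6861 × (1/250 + 1/1550)] = 0.03163.
- Alternative SE = √(0.24/250 + 0.21/1550) = 0.03310.
- z = (0.10 − 1.96 × 0.03163)/0.03310 = 1.148, so power is 87.5%.

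Simulating the chi-square also gives 87.5%. The printed 87% is correct for this test.

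**Step 2: group-by-time contrast, logit scale, b = 30%.** The effect is logit(0.40) − logit(0.30) = 0.442. With follow-up rate p, the variance per patient is 1/[b(1−b)] + 1/[p(1−p)] − 2ρ/√[b(1−b)p(1−p)]. Divide by the group size, add the two groups, take the square root for the SE, and power is Φ(0.442/SE − 1.96).

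- ρ = 0: positives 4.762 + 4.167 = 8.929; negatives 4.762 + 4.762 = 9.524; SE = √(8.929/250 + 9.524/1550) = 0.2046; z = 0.200; power 58%.
- ρ = 0.3: positives 8.929 − 2.673 = 6.256; negatives 9.524 − 2.857 = 6.667; SE = 0.1712; z = 0.620; power 73%.
- ρ = 0.5: 4.474 and 4.762; SE = 0.1448; z = 1.091; power 86%.

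A 20,000-replicate simulation of paired binary data agrees within about a point (58%, 73%, 87%). On the risk-difference scale the same three cases give 59%, 75% and 87%.

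**Step 3: dependence on the assumed baseline and scale.**

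| Baseline, both groups | Logit power, ρ = 0 to 0.4 | Risk-difference power, ρ = 0 to 0.4 |
|---|---|---|
| 30% | 58% to 80% | 59% to 81% |
| 20% | 52% to 73% | 65% to 85% |
| 10% | 38% to 54% | 73% to 89% |

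A lower baseline hurts on the logit scale, where 1/[b(1−b)] grows, and helps on the risk-difference scale, where b(1−b) shrinks. The correlation needed to reach 87% is 0.51 (logit) or 0.49 (risk difference) at b = 30%. At b = 10% it is 0.80 or 0.34.

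**Step 4: a 3-month comparison adjusted for prior testing.** As an approximation on the risk-difference scale, the SE is 0.03310 × √(1 − ρ²).
- ρ = 0: 0.03310, power 86%.
- ρ = 0.3: 0.03157, power 89%.
- ρ = 0.5: 0.02866, power 94%.

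Simulating the adjusted model gives about 88%, 90% and 95%, each to within about a point.

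**The case against.** The strongest reply is that nothing is wrong with the 87%. Section 8.1 names its inputs and its test, and the figure reproduces. Section 2.1 sets the comparison at three months and does not mention change for the renal endpoint. Section 3.4 explains the improvement as 40% in positives against 30% in negatives, so the increase in Sub-Aim 3.1 can be read as higher in positives than in negatives. Section 8.2 lists chi-square for categorical group comparisons. The GEE clause is in a general methods paragraph and also covers blood pressure control status and the comparison with controls. Sizing blood pressure on change and renal testing on a proportion may have been deliberate.

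Most of this stands, and it rules out three stronger readings that a reader might infer:

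- That the 87% is miscalculated. It is not.
- That the plan commits its primary renal analysis to a difference in change. It designates no primary renal analysis, and a 3-month chi-square is a fair reading.
- That the change contrast has 58% to 80% power unless the correlation reaches about 0.5. Those figures need a 30% baseline in both groups, which the documents do not supply. Their only background rate, 1 in 25, is from a Medicare population (Section 1.1). At 4% and zero correlation, power would be 22% on the logit scale and 80% on the risk-difference scale.

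The harm is also conditional. Section 8.1 ties the 87% to the chi-square by name, so a careful reader need not misapply it.

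The reply does not remove the gap. The one method named for renal testing is a test of change, it has no power statement, and the plan gives nothing from which its power could be worked out.

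**Conclusion.** The concern holds as a mismatch between a power figure and a named model. The 87% (87.5% recomputed) belongs to a one-time comparison of 40% with 30% and cannot be read across to the GEE test of change. With 30% tested at baseline in both groups, that test has logit-scale power of about 58%, 73% and 86% at correlations 0, 0.3 and 0.5, which is 87.5 − 57.9 = 29.6, 87.5 − 73.2 = 14.3 and 87.5 − 86.2 = 1.3 points below the chi-square. Across baselines of 10% to 30%, correlations of 0 to 0.4 and both scales, it runs from about 38% to 89%, so a shortfall is likely over much of that range but not certain. All of these figures rest on the assumptions listed in the working. If the 3-month comparison is the intended main analysis, the 87% applies to it as printed.

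**What to change.** In Section 8.1, state that the 87% applies to the 3-month comparison of APOL1 positives with negatives.

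In Section 8.2, make the renal analysis a logistic (or GEE) model of testing by 3 months, with APOL1 status as the term of interest and pre-randomization testing as a covariate. Section 6.7 already extracts the 12 months before randomization, so the covariate is available. A covariate need not cover a window of the same length as the outcome, whereas a change score would require that. Power is about 86% to 88% at zero correlation and rises with correlation, so the printed figure is roughly kept or exceeded.

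Keep the change contrast as a supportive analysis. If its power is printed, give the assumed baseline rate, correlation and scale beside it.

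The cost is wording only, with no new data or participants. The downside is that the adjusted model estimates the adjusted 3-month difference, not the difference in change. If the investigators want the difference in change as the main result, they should say so and accept a power statement that may be less favourable than 87%.
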